6.2.1.4 Dosage Adjustments, Delays, Rules for Withholding or Restarting, Permanent Discontinuation

Treatment Interruption

Significant events attributed to the drug or infusion may require treatment interruption.

Note: The definition of treatment interruption may include interruption of infusion or delay of the subsequent dose.

Events leading to treatment interruption may include:

- The subject experiences a grade \geq 3 adverse event related to the infusion/drug
- Technical problem with the syringe/infusion pump/syringe pump
- The investigational product is incorrectly prepared or administered (eg, overdose)

Treatment Interruption and Re-Start in Case of Adverse Events During the Infusion

Treatment must be modified for any clinically relevant (as determined by investigator) adverse events that occur during the infusion and are related to investigational product, as follows:

- grade 2 adverse event: **Prior to next dose, adverse event must resolve to grade 1 or less for at least 24 hours, including isolated lab abnormalities and organ toxicity labs**
- grade 3 adverse event: Interrupt the infusion until the adverse event is grade ≤ 1 **for at least 24 hours prior to the next dose of AMG 427**. Restart at the same dose if interruption is ≤ 72 hours. If interruption is > 72 hours, restart at a lower dose (last safe dose as **recommended** by DLRT or a lower dose). If the adverse event is a DLT, follow Section 6.2.1.3 for management of DLT.
 - **Subjects who experience CRS grade 3 should have next dose delayed until CRS resolves to grade ≤ 1 for at least 24 hours prior to the next dose of AMG 427 (including isolated lab abnormalities and organ toxicity labs, except for liver function tests, which must resolve to grade 2 or less), and should have next dose(s) reduced by one-half or more, if given on scheduled day (please consult with the study medical monitor).**
- grade 4 adverse events during the infusion: Permanently discontinue the investigational product

The Amgen medical monitor has to be consulted prior to a planned re-start.

In case of a dose reduction, re-escalation to the target dose can be considered for the next infusion if treatment at the lower dose has been well tolerated. An intermediate dose level may be administered prior to stepping up to the target dose after consultation with the Amgen medical monitor.

The subject should be hospitalized for at least 72 hours after re-start of the infusion.

If possible, the number of infusions at the target dose in a cycle should sum up to the planned number of infusions. In this case, the cycle would still be DLT-evaluable.

Permanent Discontinuation

A subject will permanently discontinue treatment with investigational product in the event of:

- dose-limiting or other unmanageable toxicity
 - except subjects who have experienced a DLT at a certain dose level may continue to receive AMG427 at a lower dose, if AMG 427 has shown efficacy in the specified subject, and the subject's adverse events have reduced to grade 2 or lower, and after discussion with the Amgen Medical Monitor.
- grade 4 CRS
- grade 2 or 3 CRS meeting any of the criteria listed below:

- grade 2 or 3 CRS that does not improve to \leq grade 1 within 7 days
- grade 3 CRS that does not improve to \leq grade 2 within 5 days
- grade 3 CRS at the initial run-in dose for a cycle (ie, at the MTD1) (for cohorts with dose step only)
- If a subject experiences 2 separate grade 3 CRS events
- disease progression as defined by revised IWG response criteria ([Appendix E](#))
- withdrawal of subject's consent to treatment
- subject or investigator not compliant with the study protocol
- occurrence or progression of a medical condition, which in the opinion of the investigator, should preclude further participation of the subject in the study
- a treatment interruption of more than 21 days due to an adverse event not clearly related to the underlying disease (except neutropenia)
- occurrence of a CNS-related adverse event considered related to AMG 427 by the investigator and meeting 1 or more of the following criteria:
 - more than 1 seizure
 - a CNS-related adverse event grade 4
 - a CNS-related adverse event leading to treatment interruption that needed more than 1 week to resolve to grade \leq 1
- graft-versus-host disease
- investigator's decision that a change of therapy (including immediate HSCT) is in the subject's best interest

Females who become pregnant while on study through 4 weeks after receiving the last dose of study drug will not receive subsequent scheduled doses and will be followed for safety until the end of study visit.

Males on study through 4 weeks after receiving the last dose of study drug must practice sexual abstinence or use a condom while on study through 4 weeks after receiving the last dose of study drug.

All reasons for treatment discontinuation should be clearly and concisely documented in the eCRF. If a subject has not continued to present for study visits, the investigator should determine the reason and circumstances as completely and accurately as possible.

In any case of premature treatment discontinuation, the investigator should make every effort to perform all examinations scheduled for the end of treatment (EOT) and SFU visits. These data should be recorded, as they comprise an essential evaluation that should be performed prior to discharging any subject from the study and to allow for the evaluation of the study endpoints.

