6.4.2 Criteria for Conditional Withholding of AMG 427 due to Potential Hepatotoxicity

For subjects who do not meet the criteria for permanent discontinuation of AMG 427 outlined above and have no underlying liver disease and eligibility criteria requiring normal transaminases and TBIL at baseline or subjects with underlying liver disease and baseline abnormal transaminases, the following rules are recommended for withholding of Amgen investigational product and other protocol-required therapies:

- Elevation of either AST or ALT according to the following schedule:
 - Any AST or ALT elevation: $> 8 \times \text{ULN}$ at any time
 - Any AST or ALT elevation: $> 5 \times \text{ULN}$ but $< 8 \times \text{ULN}$ for ≥ 2 weeks
 - Any AST or ALT elevation: $> 5 \times \text{ULN}$ but $< 8 \times \text{ULN}$ and unable to adhere to enhanced monitoring schedule
 - Any AST or ALT elevation: $> 3 \times \text{ULN}$ with clinical signs or symptoms which are consistent with hepatitis (such as right upper quadrant pain/tenderness, fever, nausea, vomiting, or jaundice).
- OR: TBIL $> 3 \times \text{ULN}$ at any time
- OR: ALP $> 8 \times \text{ULN}$ at any time

AMG 427 should be withheld pending investigation into alternative causes of the laboratory elevations. If the investigational product is withheld, the subject is to be followed according to recommendations in [Appendix A](#) for possible DILI. Rechallenge may be considered if an alternative cause for impaired liver tests (ALT, AST, ALP) and/or elevated TBIL level is discovered and the laboratory abnormalities resolve to normal or baseline (Section [6.4.3](#)).

Discontinuation of the product should be considered and the decision to re-challenge should be discussed with the Amgen medical monitor before re-initiating treatment with investigational product.

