
Fever (temperature $\geq 38^{\circ}\text{C}$) with:
 
 • Hypotension not requiring vasopressor AND/OR • Hypoxia requiring low-flow ≤ 6 L/min nasal cannula or blow-by 	
Administer:
 
 • Symptomatic treatment (eg, paracetamol/ acetaminophen for fever) • Tocilizumab^b 8 mg/kg IV over 1 hour (not to exceed 800 mg). If no clinical improvement in signs and symptoms of CRS after the first dose, repeat tocilizumab every 8 hours (maximum 3 doses in a 24-hour period; maximum total of 4 doses). If improving discontinue tocilizumab. • Dexamethasone 10 mg IV up to 3 times a day. Continue corticosteroids until the severity is grade 1 or less. If not improving manage as grade 3 below. • Supplemental oxygen when oxygen saturation is $< 90\%$ on room air • Intravenous fluids or low dose vasopressor for hypotension when systolic blood pressure is < 100 mmHg. Persistent tachycardia (eg, > 120 bpm) may also indicate the need for intervention for hypotension. 
Monitor for CRS symptoms including vital signs and pulse oximetry at least Q2 hours for 12 hours or until resolution to CRS grade ≤ 1 for at least 24 hours prior to the next dose of AMG 427.
 
For subjects with extensive co-morbidities or poor performance status, manage per CRS guidance below.
	
If hypotension worsens or persists 2 hours after adequate medical management, interrupt AMG 427 until CRS is grade ≤ 1 for at least 24 hours prior to the next dose of AMG 427. Refer to re-start criteria below for CRS grade 3. If symptoms progress to grade 3 criteria, see row below. Permanently discontinue AMG 427 if there is no improvement to CRS \leq grade 1 within 7 days.

Footnotes defined on next page of the table

Table 7. Management of Cytokine Release Syndrome

Description of CRS Severity ^a	Minimum Expected Intervention	Instructions for Interruption of AMG 427

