
Fever (temperature $\geq 38^{\circ}\text{C}$) with:
 
 • Hypotension requiring a single vasopressor (not including vasopressin) AND/OR • Hypoxia requiring high-flow (> 6 L/min) nasal cannula, facemask, nonrebreather mask, or Venturi mask 	
Admit to intensive care unit (ICU) for close clinical and vital sign monitoring per institutional guidelines.
 
 • Tocilizumab^b 8 mg/kg IV over 1 hour (not to exceed 800 mg). If no clinical improvement in signs and symptoms of CRS after the first dose, repeat tocilizumab every 8 hours (maximum 3 doses in a 24-hour period). If improving discontinue tocilizumab. 
Administer dexamethasone 10-20 mg up to three times a day. If improving manage as appropriate grade above and continue corticosteroids until severity is grade 1 or less, then taper as clinically appropriate.
 
Consider methylprednisolone up to 1000 mg or as per institutional practice.
	
Subjects who experience CRS grade 3 should have next dose delayed until CRS resolves to grade ≤ 1 for at least 24 hours prior to the next dose of AMG 427 (including isolated lab abnormalities and organ toxicity labs, except for LFTs, which must resolve to grade 2 or less), and should have next dose(s) reduced by one-half or more, if given on scheduled day (please consult with the study medical monitor).
 
Permanently discontinue AMG 427 if there is no improvement to CRS \leq grade 2 within 5 days or CRS \leq grade 1 within 7 days.
 
Permanently discontinue AMG 427 if CRS grade 3 occurs at the initial run in dose (ie, at MTD1).

Footnotes defined on next page of the table

Table 7. Management of Cytokine Release Syndrome

Description of CRS Severity ^a	Minimum Expected Intervention	Instructions for Interruption of AMG 427

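### The liver-test level required before the next AMG 427 dose after CRS is contradictory: two routes for grade 2 CRS disagree, and precedence against the hepatotoxicity rules is not stated.

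*Protocol*

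**What the plan says.** Four places bear on the liver-test level needed before the next dose.

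- **Protocol 6.2.1.4, grade 2 bullet.** For a related, clinically relevant grade 2 event during the infusion: "adverse event must resolve to grade 1 or less for at least 24 hours, including isolated lab abnormalities and organ toxicity labs". There is no liver exception.
- **Protocol 6.2.1.4, grade 3 bullet and its CRS sub-bullet.** The general rule is "Interrupt the infusion until the adverse event is grade ≤ 1", held for 24 hours. The sub-bullet for grade 3 CRS keeps that level for CRS and other laboratory values, "except for liver function tests, which must resolve to grade 2 or less". It adds that subjects "should have next dose(s) reduced by one-half or more, if given on scheduled day".
- **Protocol 6.6, Table 7.** The grade 3 row repeats the sub-bullet: "except for LFTs, which must resolve to grade 2 or less". The grade 2 row interrupts dosing when hypotension worsens or persists despite management, and then says: "Refer to re-start criteria below for CRS grade 3". The text directly after the table sends re-start after CRS to the general guidance in 6.2.1.4.
- **Protocol 6.4.2.** Withholding is recommended for AST or ALT above 8 x ULN at any time, or above 3 x ULN "with clinical signs or symptoms which are consistent with hepatitis (such as right upper quadrant pain/tenderness, fever, nausea, vomiting, or jaundice", among other triggers. Rechallenge may be considered if an alternative cause is discovered "and the laboratory abnormalities resolve to normal or baseline". Section 6.4.3 adds permanent discontinuation if signs or symptoms recur on rechallenge.

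**The concern.** An investigator who holds a subject after grade 2 CRS, with liver tests still raised, needs one answer on whether the next dose may be given. The protocol sends that investigator along two routes that end at different liver-test levels. A third set of rules may apply as well, and its relation to the other two is not stated.

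The combination is foreseeable. Section 6.6 lists transaminitis among the signs of CRS. The DLT definition in 6.2.1.3 has a specific exception for grade 3 transaminitis with grade 2 CRS.

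The first stake is hepatic safety on re-exposure, in a toxicity that has been fatal once in this trial. The current amendment was written to tighten CRS risk mitigation, and its rationale names dose-modification criteria among the changes. The second stake is consistency: sites that read different passages would give different cycle 1 exposure to subjects at the same nominal dose level.

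**Working it through.** No formula applies, so the check sets the rules side by side.

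| Place | Subjects covered | Liver tests before next dose | Attached condition |
|---|---|---|---|
| 6.2.1.4, grade 2 bullet | Related grade 2 event during infusion | Grade 1 or less, 24 h | None on dose |
| 6.2.1.4, grade 3 CRS sub-bullet | Grade 3 CRS | Grade 2 or less | Next dose(s) reduced if given on scheduled day |
| Table 7, grade 3 row | Grade 3 CRS | Grade 2 or less | Same as sub-bullet |
| Table 7, grade 2 row | Grade 2 CRS, hypotension worsening or persisting | Grade 2 or less, by cross-reference | CRS at grade 1 or less for 24 h |
| 6.4.2 | Any subject meeting its triggers | Normal or baseline, plus alternative cause | Discuss with medical monitor |

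**Grade 2 CRS.** Take a subject with grade 2 CRS during the infusion and persistent hypotension. CRS has since been at grade 1 or less for 24 hours, and AST is at CTCAE grade 2.

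1. Table 7, grade 2 row to grade 3 criteria: the liver condition is met and the next dose may be given.
2. Text after Table 7 to 6.2.1.4, grade 2 bullet: the liver condition is not met and the dose waits.
3. If a 6.4.2 trigger was also met during the episode, the subject waits for normal or baseline values and needs an alternative cause.

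Routes 1 and 2 contradict each other for this subject. The cross-reference in route 1 also leaves unsaid whether the dose reduction attached to grade 3 CRS carries over to grade 2.

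**Grade 3 CRS.** With the same AST, the 6.2.1.4 sub-bullet and Table 7 agree that the liver condition is met, with the reduced next dose(s) if given on the scheduled day. Read alone, 6.2.1.4 is therefore looser on liver tests after grade 3 CRS than after a grade 2 event. Under Table 7 both grades share one level, so the difference disappears for the subjects its grade 2 row covers.

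**Overlap with 6.4.2.** The 8 x ULN trigger has no symptom condition, so it can be met during CRS. The 3 x ULN trigger needs signs consistent with hepatitis. Fever is one listed example, and fever is also a grading criterion for CRS in Table 6. The alternative causes listed in 6.4.1 include hypotension and hypoxia to the liver but do not name CRS, and the list is open-ended. No passage ranks 6.4.2 against the CRS re-start rules.

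**Size.** CRS of any grade was reported in 42 of 53 subjects (42/53 = 79.2%), and 2 of those 53 received etanercept only. Section 2.2.4 also lists grade 3 or higher ALT increase in 2 subjects (5.9%). That percentage fits a denominator of 34 (2/34 = 5.9%) and not 53 (2/53 = 3.8%), so the two figures do not share a base. No table crosses CRS grade with liver grade. The frequency of the disputed situation cannot be derived.

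The documents give no ULN multiples for CTCAE grades, so grade 2 cannot be placed numerically against the 3 x and 8 x ULN triggers from the documents alone. The ordering (normal or baseline, grade 1 or less, grade 2 or less) needs no such figure.

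**The case against.** The best defence is that the system is more orderly than it looks.

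- **Grade 3 CRS is consistent.** The 6.2.1.4 sub-bullet and Table 7 match, and the sub-bullet reads naturally as an exception to its parent. This stands. A reader might infer that three sections set three different levels across the board; the documents do not support that.
- **A governing section is named.** The text after Table 7 sends re-start after CRS to 6.2.1.4, so it would be wrong to infer that nothing governs. This stands in part: that pointer is what conflicts with the one inside the grade 2 row, and it is silent on 6.4.2.
- **Worse CRS is not re-dosed more freely overall.** The grade 1 rule is a general adverse-event bullet, the looser liver level comes with a reduced dose if given on schedule, and Table 7 aligns the two grades. This stands: the inversion is confined to two bullets of 6.2.1.4.
- **6.4.2 is a general hepatotoxicity rule.** It is worded as a recommendation. It would be an overreading that any CRS with enzymes above 3 x ULN triggers it. The signs must be consistent with hepatitis, and Table 6 counts fever towards CRS only when no other cause explains it. This stands, but the 8 x ULN trigger needs no such sign.
- **The medical monitor must be consulted before re-start.** True, but the monitor reads the same conflicting text.
- **DLT-evaluability is protected.** Under 6.2.1.4 the cycle stays evaluable if the planned number of target-dose infusions is reached, and Section 3.4 replaces non-evaluable escalation subjects. This largely stands, so loss of evaluable subjects should not be claimed as the main consequence.

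**Conclusion.** The contradiction is real but narrower than a quick reading suggests. For grade 2 CRS, two stated pointers lead to different liver-test levels for the same subject. For CRS of any grade that also meets a 6.4.2 trigger, precedence and the status of CRS as an alternative cause are not stated. For grade 3 CRS without such a trigger, the CRS-specific rules agree.

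The conclusion assumes that the grade 2 row's pointer means the grade 3 row of Table 7, and that the pointer after the table brings grade 2 CRS under the grade 2 bullet of 6.2.1.4. Both are the plain readings.

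The size is unknown. A reader might take the 79.2% CRS figure as the magnitude, but it counts CRS of any grade with no regard to liver tests. The point needs correcting because it governs re-exposure after a common and once fatal toxicity, whatever its frequency. Nothing here bears on which level is right.

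**What to change.** Reconcile 6.2.1.4, Table 7 with the re-start text after it, 6.4.2 and 6.4.3, so that:

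- one liver-test re-start rule applies to each CRS grade, stated once and referred to elsewhere;
- the pointer in the Table 7 grade 2 row and the pointer after the table lead to the same rule, and it is clear whether the attached dose reduction goes with it;
- the protocol states which section takes precedence when a 6.4.2 trigger is met during CRS;
- the protocol states whether CRS counts as an alternative cause under 6.4.2.

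The clinical team sets the levels. The cost is protocol wording in the next amendment and a letter to sites, with no effect on sample size or on data already collected.

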- The MRD+ group will use Schedule C for all cycle collections and [Table 22](#) for additional whole blood MRD collection, or [Table 23](#), as applicable.

After reviewing additional PK, safety, and efficacy data, the DLRT may recommend the administration of additional doses on day 12 and 19, to comprise a 4-week cycle with doses on either D1/D5/D12/D19 or D1/D3/D5/D8/D12/D19. Once the DLRT recommends a 4 or 6 dose schedule (D1/D5/D12/D19 or D1/D3/D5/D8/D12/D19), all subsequent cohorts will be treated with a 4 or 6 dose schedule. If on Schedule A (**CLOSED**) or C, all subjects will be pre-treated with an 8 mg dose of IV dexamethasone within 1 hour prior to D1, D3 (if applicable), D5, and D8 (if applicable) AMG 427 doses and each dose step. A dose step is any AMG 427 dose that is higher for a given subject than the subject has previously received. A dose step will be triggered by the observation of CRS or infusion related reaction at the first dose (see example in [Figure 2](#)). Dose steps may occur at the D3, D5, D8, D12, or D19. Each cycle will last for approximately 14 days for cohorts receiving 2 or 4 doses (D1/D5 or D1/D3/D5/D8), and approximately 28 days for cohorts receiving 4 or 6 doses (D1/D5/D12/D19 or D1/D3/D5/D8/D12/D19). Subjects will be assessed for DLTs for 28 days. Cycles will be followed by a treatment-free interval for 1-2 weeks (depending on response), which may be extended for up to 7 weeks or longer for the cohorts at higher doses, based on a dose level review meeting (DLRM) recommendation. The D3, D5, D8 doses, and the D12, D19 doses (if applicable) may be at the same dose as the preceding dose or may be at a higher dose level (dose step). This will be based on tolerability of the lower dose level and other clinical signs, pharmacological, and PD results and will be recommended by the DLRT. For a schematic description of the different dose step options see [Figure 2](#) in Section 3.1. For logistical reasons, there is a $\pm 1 - 3$ day window for dosing days.

Dose Escalation Cohorts

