Administration of a prophylactic steroid dose (8 mg IV dexamethasone) within 1 hour prior to start of AMG 427 dose on days 1, 3, 5, and 8 and prior to each dose step of AMG 427, to mitigate CRS, is mandatory. There is a \pm 1-3 day window for dosing visits.

[figure not shown]
Other dose level(s) of dexamethasone may be evaluated as necessary.

[figure not shown]
All other dosing rules, including dose limiting toxicities and treatment interruption, withholding, rechallenge, and permanent discontinuation apply as stated in Sections [6.2-6.6](#).

[figure not shown]
The estimate of the MTD(s), or the estimate of each MTD if step dosing is used, will use the BLRM design. Dose escalation will proceed using 2 parts: single subject cohorts and multiple subject cohorts.

[figure not shown]

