3.1.1.1 FIH Group

The FIH group will evaluate AMG 427 administered as a short-term IV infusion in adult subjects with R/R AML. In escalation, approximately 90 subjects with R/R AML will be a part of FIH cohorts [REDACTED] (Table 4). Approximately 25 subjects with R/R AML will receive etanercept for CRS prophylaxis 2 days prior to their cycle and follow guidance below. **The option for group extension may be available, either at sponsor discretion or if recommended by the DLRT based on the review of the emerging safety data. The sponsor will notify sites, if applicable, when the extended slots for a group are open for enrollment after DLRT has confirmed the dose level is safe.**

3.1.1.2 eIV Infusion Group

The eIV group will evaluate AMG 427 administered as an eIV infusion in approximately 10 subjects with R/R AML. The study will be conducted in dose escalation, to explore and identify if alternative dosing of AMG 427 leads to an improved benefit/risk profile. The option for group extension may be available, either at sponsor discretion or if recommended by the DLRT based on the review of the emerging safety data. The sponsor will notify sites, if applicable, when the extended slots for a group are open for enrollment after DLRT has confirmed the dose level is safe. If improvement is seen in the benefit/risk profile for these subjects, eIV administration may be implemented in the ongoing FIH (short IV) dose escalation cohorts, as well as expansion cohorts.

Utilizing Schedule C, the eIV study design will consist of eIV and short IV infusions of AMG 427 administered on days 1 **and** 2, 3, 5, and 8.

- Days 1 and 2 will consist of the D1 dose administered as an eIV infusion over 48 hours (approximately 12-hour IV bag changes).
- Day 3 will consist of the D3 dose administered as an eIV infusion over 24 hours (approximately 12-hour IV bag changes).
- The remaining 2 doses (D5 and D8) will be regular short IV infusions (approximately 90 minutes) on day 5 and day 8.

The first eIV group will start at a DLRT-approved dose level from the FIH group as described in Section [6.2.1.1](#).

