
 • Fever (temperature $\geq 38^{\circ}\text{C}$) with: • Hypotension requiring multiple vasopressors (excluding vasopressin) AND/OR • Hypoxia requiring positive pressure (eg, CPAP, BiPAP, intubation and mechanical ventilation) 	
Admit to ICU for close clinical and vital sign monitoring per institutional guidelines.
 
 • Tocilizumab^b 8 mg/kg IV over 1 hour (not to exceed 800 mg). If no clinical improvement in signs and symptoms of CRS after the first dose, repeat tocilizumab every 8 hours (maximum 3 doses in a 24-hour period). If improving discontinue tocilizumab. 
Administer methylprednisolone up to 1000 mg once per day for 3 days. If improving manage as appropriate grade above and continue corticosteroids until severity is grade 1 or less then taper as clinically appropriate.
 
If not improving consider methyl prednisolone 1000 mg two to three times a day or alternate therapy.
	
Immediately stop the infusion and permanently discontinue AMG 427 therapy.

Page 4 of 4

BiPAP = bilevel positive airway pressure; CPAP = continuous positive airway pressure; CRS = Cytokine Release Syndrome; ICU = intensive care unit;

IL-6 = interleukin 6; IL-6R = interleukin 6 receptor; IV = Intravenous; LFT(s) = liver function test(s); MTD = maximum-tolerated dose

^a Grading system for CRS (Lee et al, 2019)

^b If tocilizumab is not available, another IL-6/IL-6R inhibitor eg, siltuximab may be used per institutional practice for CRS.

Re-start of treatment after CRS:

Please refer to the general guidance for re-start of treatment after adverse events in Section [6.2.1.4](#)

For grade 3 and 4 CRS, please see Section [6.2.1.3](#) for DLT considerations.

Immune-effector Cell-associated Neurotoxicity Syndrome (ICANS):

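### After non-DLT grade 3 CRS the dose cut is written only for a next dose given on its scheduled day; a short delay is left with the full dose, two conflicting rules, or no stated dose

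*Protocol*

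**What the plan says.** - **CRS rule.** In Section 6.2.1.4 the CRS sub-bullet delays the next dose until CRS has been grade 1 or lower for 24 hours. It adds that subjects "should have next dose(s) reduced by one-half or more, if given on scheduled day (please consult with the study medical monitor"). The grade 3 row of Table 7 repeats the condition: subjects "should have next dose(s) reduced by one-half or more, if given on scheduled day". Neither place gives a dose for a late infusion.
- **General rule.** The grade 3 bullet above it covers adverse events of any kind: "Restart at the same dose if interruption is ≤ 72 hours. If interruption is > 72 hours, restart at a lower dose". A note in the same section says: "The definition of treatment interruption may include interruption of infusion or delay of the subsequent dose".
- **Link to CRS.** After Table 7, Section 6.6 says of re-start after CRS: "Please refer to the general guidance for re-start of treatment after adverse events in Section" 6.2.1.4. It adds no dose of its own.
- **Flat dosing.** Under the Synopsis study design, later doses in a cycle "may be at the same dose as the preceding dose or may be at a higher dose level (dose step").
- **Timing.** Section 3.1.1 allows a plus or minus "1-3 day window for dosing visits". No section says whether a dose inside that window counts as given on its scheduled day.
- **eIV.** Section 3.1.1.2: "Days 1 and 2 will consist of the D1 dose administered as an eIV infusion over 48 hours". The D3 dose then runs for 24 hours.
- **DLT status.** Under Section 6.2.1.3, grade 3 CRS is a DLT if it is not grade 2 or lower within 5 days or grade 1 or lower within 7 days, if it is a second separate event, or if it occurs at a defined MTD1 run-in dose. This point concerns the remaining, non-DLT events.

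**The concern.** After severe CRS, slower recovery should never lead to a larger next dose. Here the cut is tied to the dose being on time, which means to quick recovery, and the only rule written for a short delay repeats the same dose. Two sites could give like subjects different doses and both be following the text.

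The rule matters because Amendment 7 added CRS dose-modification measures after a fatal grade 5 CRS event and a partial clinical hold. The eIV group, where the general rule applies most directly, enrolls first (Section 2.4.3).

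**Working it through.** The plan gives no figure to reproduce here, so the check is to apply the rules to each case.

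**1. Three readings of a delay of up to 72 hours**

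| Reading | Result for the delayed dose |
|---|---|
| Delay is an interruption; a late dose is not on its scheduled day | Same dose |
| Delay is an interruption; the 1-3 day window counts as the scheduled day | Halving and same dose both apply; no stated precedence |
| The general rule covers only events during infusion, or the CRS sub-bullet displaces it | No stated dose |

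**2. Size on the first reading.** Let the provoking dose be 1 and the planned next dose be r. I assume that the same dose means the provoking dose and that halving is taken from the planned dose.

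- On time: at most r/2. Delayed up to 72 hours: 1. Ratio: at least 2/r.
- r = 1 (flat): 1/0.5 = 2.0
- r = 1.5: 1/0.75 = 1.33
- r = 2: 1/1 = 1.0, so no inversion at 2-fold or above

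Dose levels are redacted, so r is unknown.

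**3. Which recoveries fall in the band (short infusions).** Let g be the gap between doses. An on-time dose needs grade 1 or lower by g − 24 hours. The protocol does not say when the 72-hour clock starts.

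| Gap | Clock from missed dose: g − 24 to g + 72 − 24 | Clock from prior infusion: g − 24 to 72 − 24 |
|---|---|---|
| 48 h (D3 to D5; D1 to D3 if D1 is not a defined MTD1 run-in dose) | over 24 to 96 h | over 24 to 48 h |
| 72 h (D5 to D8) | over 48 to 120 h | none |

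These times to grade 1 or lower are all inside the 7-day (168-hour) DLT limit. Section 6.2.1.3 also exempts grade 3 CRS resolving within 12 hours from its non-hematologic DLT rule. If that 12-hour limit decides DLT status, onset within 12 hours gives resolution by 12 + 12 = 24 hours. The 48-hour-gap band is then empty for those events, apart from slow laboratory recovery.

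**4. eIV.** Suppose the 48-hour D1 infusion stops at hour h and CRS reaches grade 1 or lower x hours later. Applying the 24-hour requirement, the earliest restart is h + x + 24. The interruption is x + 24 hours, so same-dose restart applies for x up to 48. No permissive definition is needed, because the infusion itself was interrupted. If the remaining 48 − h hours run at an unchanged rate, D1 ends at (h + x + 24) + (48 − h) = 72 + x hours. D3 was due at 48 hours, so it starts 24 + x hours late: at most 72 hours when x is at most 48, which is within +3 days. Whether D3 is then halved again depends on the undefined scheduled day.

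**5. Frequency.** Section 2.2.4 lists grade 3 or higher CRS in 2 subjects, printed as 5.9%. That matches 2/34 (95% CI 0.7% to 19.7%). With the 53 exposed subjects it would be 2/53 = 3.8% (0.5% to 13.0%). SAP Section 9.6.2 shows that some cohorts were graded on an older scale, and all these subjects had R/R AML.

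**The case against.** The strongest reply is that the inversion is only one reading. A 3-day window equals 72 hours, so if a dose inside it counts as on schedule, the rules could fit together: halve up to 72 hours, go lower beyond. The Schedule C footnotes also let the DLRT move D3, D5 and D8 within that window. A specific CRS rule would normally override the general bullet above it. The general bullet is headed for events during the infusion and reaches later CRS only through a permissive note. This stands as far as it goes. But the text defines neither term and states no precedence, and the footnotes concern DLRT recommendations, not individual subjects.

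It could also be said that a delay lowers residual exposure, so a full dose is acceptable. No section gives that rationale, and it fits badly with requiring a lower dose after more than 72 hours.

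The safeguards are real: monitor consultation before any re-start, 24 hours at grade 1 or lower, 72-hour hospitalization, and stopping after a second grade 3 CRS. They limit the harm, but none prescribes a lower dose for a short delay.

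A further fair point concerns the remedy. Halving alone, taken from the planned dose, would permit r/2. At r = 3 that is 1.5 times the provoking dose, against 1.0 under the present same-dose rule. A cap is needed.

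**Conclusion.** The gap is real: after non-DLT grade 3 CRS, no reduced dose is written for a delay of up to 72 hours. On the plain reading this is an inversion of at least 2-fold under flat dosing, shrinking to none at planned steps of 2-fold. On the other readings it is a conflict or an unstated dose. The result assumes a non-DLT event that is not at a defined MTD1 run-in dose; the documents do not say whether the eIV D1 dose is one.

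Three stronger conclusions are not supported:

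- A reader might infer that the protocol requires the full dose after slow recovery. It does not: the monitor must be consulted and may choose a lower dose.
- A reader might infer that D3 always misses its day after an interrupted eIV infusion. That assumes an unchanged rate, which no section requires, and ignores the window.
- A reader might project a count of affected subjects. Two events with an uncertain denominator cannot carry one, and only part of any such events would fall in the band.

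The number is unknown and probably small. The change is still worth making, because it closes a hole in a CRS safeguard for little cost.

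**What to change.** In Section 6.2.1.4 and the grade 3 row of Table 7:

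1. Delete the scheduled-day condition. State that the next dose in the same cycle after non-DLT grade 3 CRS, on time or delayed, is at most one-half of the planned dose and never above the dose that provoked the CRS.
2. State that same-dose restart for interruptions of 72 hours or less does not apply to grade 3 CRS, including an eIV infusion stopped for it.
3. For more than 72 hours, keep the last safe dose or lower, also no higher than the limit in item 1.

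In the notation above, the limit becomes the smaller of r/2 and 1, whatever the delay: 0.5 at r = 1, 0.75 at r = 1.5 and 1.0 at r = 3. The inversion is gone, and no subject receives more than the provoking dose at that next infusion.

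The cost is amendment wording in two places. Some subjects reach the target dose later. Some cycles may need make-up infusions at the target dose to stay DLT-evaluable (Section 6.2.1.4). Where that is not possible, an escalation subject must be replaced (Section 3.4). This is probably a few subjects, but the number cannot be estimated reliably.
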